5.2. General Methods

Data will be presented – ie, listed and summarized – by dose group, block and overall. Data summaries may also be grouped by gender. Continuous data will be summarized comprising mean, median, standard deviation, minimum and maximum. Categorical and binary data are summarized will be done via percentages.

5.2.1. Analyses for Longitudinal Continuous Endpoints

Mixed-effect, repeated measures (MMRM) models will be used. The fixed effects of treatment, visit, treatment-by-visit interaction, age and gender will be included. Visit will be modeled as a categorical covariate. (If the model does not converge then Visit will be modeled as a continuous covariate.) Unstructured covariance matrix will be assumed for the model errors. Compound symmetry covariance matrix will be used if the model with unstructured variance covariance doesn't converge.

When modeling the change from baseline values, the variable for visit will start with the first post-baseline visit. At each visit, estimates of least square mean (LSM) values and the LSM differences between treatment groups will be derived from the model. The corresponding p-values and 95% confidence intervals will also be derived from the model.

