2.1.1. Primary Estimand(s)

The primary estimand is defined according to the primary objective and is in alignment with the primary endpoint. It includes the following 4 attributes:

- Population: Patients with achondroplasia, as defined by inclusion/exclusion criteria;
- Variable: Height Growth at 12 months;
- Height Growth = (Observed Change from Baseline in standing height (cm))/(Expected Change from Baseline (cm)[Merker et al, 2018]¹)

- Intercurrent event(s): Withdrawal and all events leading to missing data will be excluded from efficacy analysis and will not have their data imputed;
- Population-level summary: Mean Height growth at 12 months adjusted for age and gender.

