6. ANALYSES AND SUMMARIES

6.1. Primary Endpoint(s)

6.1.1. Increase in height growth above expected in reference population

6.1.1.1. Main Analysis

- Estimand strategy: Hypothetical ([Section 2.1.1](#)).
- Analysis set: FAS ([Section 4](#)).
- Analysis methodology: Change from baseline relative to Merker (2018) will be analyzed using MMRM including data from Months 3, 6, 9, and 12 with gender (and possibly age) as a covariate, subject (and/or time) as a random effect and an unstructured covariance matrix ([Section 5.2.1](#)).
- Intercurrent events and missing data: Data after study drug discontinuation and rescue will be excluded; intermediate missing values will not be imputed.
- The sample size, mean, standard deviation, median, minimum, and maximum at the baseline and postbaseline visits for observed standing height and change from baseline will be presented for each treatment arm.
- The least-squares (LS) means, the 95% confidence interval for the LS means, the difference between the LS means for each pair of treatment groups, and the corresponding 95% confidence interval will be presented for change from baseline in standing height for all postbaseline visits.

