Appendix 2.2. Endpoint Derivations

Height Growth

The primary efficacy endpoint is H defined by the following:

$$H_{ijkl} = \frac{Y_{ijkl} - Y_{i0kl}}{Z_{jl} - Z_{0l}},$$

where Y_{ijkl} is the observed standing height for the i th subject, at month j on dose k with gender factor l ($j=0$ denotes baseline measurement) and Z_{jl} is the mean expected standing height based on Merker for subject i 's age.

Mean expected standing height from Merker is sorted by 6 months up to age 4, while means expected values for children > 4 years are sorted per annum. Linear interpolation will be employed to calculate mean expected values so that mean standing height are sorted at 6 month intervals for children > 4 years. SAS code for the linear interpolation calculation will be provided in Appendix 4.

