Appendix 2.3. Definition of Protocol Deviations That Relate to Statistical Analyses/Populations

Appendix 3. Data Set Descriptions

Appendix 4. Statistical Methodology Details

Linear Interpolation

Linear interpolation will be employed to provide mean expected standing height values at 6 month interval for children $>$ age 4. The SAS code is as follows:

```
proc expand data=mydata out=LinInterp;
  convert exp_mean=linear / method=join;
  id age;
run;
```

MMRM

MMRM will be used for height growth and arm span-height difference. The SAS code is as follows:

```
proc mixed data=mydata;
  class dose gender month;
  model height = dose month gender age/s;
  random int month / type=un sub=subject;
  lsmean dose;
run;
```

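### If the primary MMRM does not converge, SAP 5.2.1 makes visit continuous: an unchecked linearity assumption that can bias the Month 12 estimate in either direction

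*SAP*

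**What the plan says.** The primary estimand in SAP 2.1.1 is a Month 12 quantity: "Population-level summary: Mean Height growth at 12 months adjusted for age and gender". The variable is a ratio of cumulative growth, "Height Growth = (Observed Change from Baseline in standing height (cm))/(Expected Change from Baseline (cm" from the reference). In Appendix 2.2 the reference height in the denominator "is the mean expected standing height based on Merker for subject i 's age". SAP 5.1 states the hypothesis at 12 months only, tested one-sided at 0.017.

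SAP 6.1.1.1 analyses this variable "using MMRM including data from Months 3, 6, 9, and 12" and points to 5.2.1 for the model. Section 5.2.1 makes visit categorical and says "The fixed effects of treatment, visit, treatment-by-visit interaction, age and gender will be included". It then gives two rules for non-convergence:

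- For the mean model: "If the model does not converge then Visit will be modeled as a continuous covariate".
- For the errors: "Compound symmetry covariance matrix will be used if the model with unstructured variance covariance doesn't converge".

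The section does not say which rule comes first. It names no quadratic or spline term and no check of linearity.

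The Appendix 4 code differs from 5.2.1. It has no dose-by-month term, requests LS means for dose only, and declares month as a class variable in "random int month / type=un sub=subject".

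**The concern.** Non-convergence of a repeated-measures model usually comes from the covariance part. The first rule changes the mean model instead. With a categorical visit and complete data, the Month 12 mean for a dose rests on Month 12 data. With a continuous visit it is read off a line fitted to all four visits, so earlier visits move it. A numerical event would then change what the primary test estimates.

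Whether this does harm depends on the path of H. Because H is cumulative, a lag of L months before a constant velocity gain contributes a term in L/t, which is curved in time. A time-varying effect cannot be ruled out. Protocol 2.2.1 reports anti-drug antibodies in 21 of 24 multiple-dose Phase 1 participants, and SAP 6.2.13 provides for looking at the effect of antibodies on PK. Neither shows that the effect wanes, but both are reasons not to assume constancy without a check.

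The missing order is a second weakness. Two analysts could fit different primary models after the same failure, in a study where only the anthropometrist is blinded to dose (Protocol 6.3).

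**Working it through.** **Inputs.** From the documents: 15 evaluable children per dose and variability 0.15 (Protocol 9.2, read here as the SD of H at Month 12); one-sided 0.017 (SAP 5.1); visits at Months 3, 6, 9 and 12 (SAP 6.1.1.1). Assumed: complete data, reference growth g of 4-5 cm/year, and height measurement SD of 0.1-0.3 cm.

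**The plan's own figure.** SE = 0.15/sqrt(15) = 0.0387. The critical value for 0.017 is 2.120, so a dose passes if its mean H exceeds 1 + 2.120 x 0.0387 = 1.082. At H = 1.5, 0.5/0.0387 = 12.9, so power is about 100%. The stated power of over 90% is met.

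**Equal weighting** (compound symmetry, or the coded random intercept and slope with month continuous). The mean visit time is 7.5 and the sum of squares is 45. The weight of visit t in the fitted Month 12 value is 1/4 + (12 - 7.5)(t - 7.5)/45. For Months 3, 6, 9 and 12 this gives -0.2, 0.1, 0.4 and 0.7.

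**Unstructured errors.** The covariance was built from a between-child component plus measurement error divided by expected growth g x t/12, with baseline error shared across visits and the Month 12 SD held at 0.15. Generalised least squares then gives weights of -0.1, 0.0, 0.3 and 0.8 throughout the assumed ranges.

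**Paths.** A lag of L months before +50% velocity gives H = 1 + 0.5(1 - L/t) for t > L, and 1 before. An effect in the first L months only gives H = 1 + 0.5 x L/t for t > L, and 1.5 before.

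| Path | H at 3, 6, 9, 12 | True H12 | Line, unstructured | Line, equal weights |
|---|---|---|---|---|
| No effect | 1, 1, 1, 1 | 1.000 | 1.000 | 1.000 |
| Constant +50% | 1.5 throughout | 1.500 | 1.500 | 1.500 |
| Linear ramp in H | 1.062, 1.125, 1.188, 1.250 | 1.250 | 1.250 | 1.250 |
| 3-month lag | 1, 1.250, 1.333, 1.375 | 1.375 | 1.400 (+0.025) | 1.421 (+0.046) |
| First 3 months only | 1.5, 1.250, 1.167, 1.125 | 1.125 | 1.100 (-0.025) | 1.079 (-0.046) |
| 6-month lag | 1, 1, 1.167, 1.250 | 1.250 | 1.250 (0.000) | 1.242 (-0.008) |
| First 6 months only | 1.5, 1.5, 1.333, 1.250 | 1.250 | 1.250 (0.000) | 1.258 (+0.008) |

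For example, the 3-month lag with unstructured errors gives -0.1(1) + 0.3(1.333) + 0.8(1.375) = 1.400. Relative to the SE, the largest shifts are 0.025/0.0387 = 0.6 and 0.046/0.0387 = 1.2.

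**Chance of passing for the early-only effect**, from Phi((H - 1)/SE - 2.120):

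- Categorical visit: 0.125/0.0387 - 2.120 = 1.11, about 86% (0.866; 0.864 with 0.05/3 as the level).
- Line, unstructured errors: the SE of the fitted value is 0.0367 to 0.0386, so 0.100/0.0386 - 2.120 = 0.47 and 0.100/0.0367 - 2.120 = 0.60, about 68-73%.

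**Covariance parameters in the Appendix 4 code.** Intercept plus four class months, unstructured, needs 5 x 6/2 = 15, plus 1 residual = 16. A 4 x 4 matrix identifies 4 x 5/2 = 10. With month continuous the code needs 3 + 1 = 4.

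**The case against.** The strongest reply is that H divides observed by expected growth over the same interval. Ordinary growth cancels, and the two cases on which the study is designed are flat lines that the fallback fits exactly. Under no effect at any visit the rejection rate stays at 0.017. That stands. A reader might infer that H is inherently non-linear and the Month 12 test therefore biased; the documents do not support this. Bias needs a curved effect path, and they describe none.

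Other stronger readings also fail:

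- *Only a velocity ratio constant from Day 1 gives a straight line.* A ratio rising linearly from 1 does so too.
- *A delayed effect is always overstated.* With a 6-month lag the shift is between 0.000 and -0.008. With a 3-month lag the true 1.375 is far above 1.082, so the dose passes either way.
- *The chance of passing falls to about 47%.* This is the equal-weight line with SE held at 0.0387: (1.0792 - 1)/0.0387 - 2.120 = -0.08. Section 5.2.1 starts from unstructured errors, and the fallback fit would have its own SE.
- *Month 12 is extrapolated.* It is an observed visit at the edge of the fitted range.
- *Making month continuous moves the coded LS means away from Month 12.* The code averages over visits with class month as well: 1.24 for the 3-month lag and 1.26 for the early-only effect in both fits. This is a separate fault in the code.
- *The fallback is likely to be used.* The count of 16 parameters against 10 makes convergence trouble with the Appendix 4 code plausible. The model in 5.2.1 needs only a 4 x 4 matrix, no failure rate can be derived from the documents, and compound symmetry might be tried first.

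The SAP also does not say how expected height is found at Month 3 and Month 9 ages between points of its 6-month reference grid. A crude lookup could bend H even with no effect. As the rule is unstated, no null bias can be claimed from it, and the figures above assume interpolation to exact age.

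**Conclusion.** The concern holds as a conditional one. After non-convergence, SAP 5.2.1 allows a primary model that assumes, without a check, that each dose's mean H is linear from Month 3 to Month 12. It does no harm under no effect, a constant +50% or a linear ramp. For effects that start or stop at about 3 months, it moves the Month 12 estimate by about 0.025 with unstructured errors and up to 0.046 with equal weighting, in either direction, against an SE of about 0.039. The decision is sensitive only for modest effects near the 1.082 threshold, such as the early-only path.

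These sizes rest on complete data, 15 children per dose, 0.15 as the SD of H at Month 12, and the assumed growth and measurement-error ranges. The probabilities are large-sample approximations. The undefined order of the two fallbacks needs no such assumptions; it is plain from the text. The change is worth making because the rule governs the primary test and the remedy is cheap.

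**What to change.** In SAP 5.2.1, delete the parenthetical sentence on continuous visit and replace the compound-symmetry sentence with:

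> Visit remains categorical with treatment-by-visit interaction in all fits. If the unstructured error matrix does not converge, only the covariance structure is simplified, in this fixed order: heterogeneous Toeplitz, then heterogeneous AR(1). If none converges, H at Month 12 is analysed by a single-visit linear model with dose, age and gender.

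Bring the Appendix 4 code into line: add the dose-by-month term, use a repeated statement for the error covariance in place of the random statement, and request the LS means at Month 12. The last-resort model is close to the Month 12 ANOVA by dose in Protocol 9.4.2, so it introduces no unfamiliar method.

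The cost is SAP wording and a few lines of code. No extra data, visits or participants are needed.

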5.3. Methods to Manage Missing Data

In general, for descriptive statistics missing values will not be imputed. In addition, for safety endpoints missing values will not be imputed. Other methods for handling missing values are discussed below. Missing data methods for baseline values are discussed in [Section 3.4](#).

5.3.1. PK and Biomarker Data

Concentrations Below the Limit of Quantification

In all data presentations (except listings), concentrations below the limit of quantification (BLQ) will be set to zero. (In listings BLQ values will be reported as “<LLQ”, where LLQ will be replaced with the value for the lower limit of quantification). For population PK modeling, BLQ will be handled by the Pfizer standard processes.

Deviations, Missing Concentrations and Anomalous Values

In summary tables of concentration data by dose, visit day and time, statistics will be calculated having set concentrations to missing if 1 of the following cases is true:

A concentration has been collected as ND (ie not done) or NS (ie no sample),

A deviation in sampling time (15% beyond the sampling time window) is of sufficient concern or a concentration has been flagged anomalous by the pharmacokineticist.

Note that summary statistics will not be presented at a particular time point if more than 50% of the data are missing.

Pharmacokinetic Parameters

Nonlinear mixed effect modeling will be performed to evaluate pharmacokinetic parameters including clearance, area under the curve at steady state over the dosing interval for reciferecept. Additional details on the population PK modeling will be described in the population modeling analysis plan.

In summary tables, statistics will be calculated by setting NC values to missing; and statistics will be presented for a particular dose with ≥ 3 evaluable measurements.

If an individual subject has a known biased estimate of a PK parameter (due for example to an unexpected event such as dosing error), this will be footnoted in summary tables and will not be included in the calculation of summary statistics or statistical analyses.

5.3.2. CHAQ

CCI

6. ANALYSES AND SUMMARIES

6.1. Primary Endpoint(s)

6.1.1. Increase in height growth above expected in reference population

6.1.1.1. Main Analysis

- Estimand strategy: Hypothetical ([Section 2.1.1](#)).
- Analysis set: FAS ([Section 4](#)).
- Analysis methodology: Change from baseline relative to Merker (2018) will be analyzed using MMRM including data from Months 3, 6, 9, and 12 with gender (and possibly age) as a covariate, subject (and/or time) as a random effect and an unstructured covariance matrix ([Section 5.2.1](#)).
- Intercurrent events and missing data: Data after study drug discontinuation and rescue will be excluded; intermediate missing values will not be imputed.
- The sample size, mean, standard deviation, median, minimum, and maximum at the baseline and postbaseline visits for observed standing height and change from baseline will be presented for each treatment arm.
- The least-squares (LS) means, the 95% confidence interval for the LS means, the difference between the LS means for each pair of treatment groups, and the corresponding 95% confidence interval will be presented for change from baseline in standing height for all postbaseline visits.

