2.1.2. Secondary Estimand(s)

The secondary efficacy estimand comprises the following 4 attributes:

- Population: Patients with achondroplasia, as defined by inclusion/exclusion criteria;
- Variable: Change from baseline to 12 months in the difference between arm span (cm) and standing height (cm);
- Intercurrent event: Withdrawal and all events leading to missing data will be excluded from efficacy analysis and will not have their data imputed;
- Population-level summary: Mean change-from-baseline of arm span/standing height difference at 12 months adjusted for age and gender.

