6.2. Secondary Endpoint(s)

6.2.1. Arm span to height/length difference

6.2.1.1. Main Analysis

- Estimand strategy: Hypothetical ([Section 2.1.1](#)).
- Analysis set: FAS ([Section 4](#)).
- Analysis methodology: Change from baseline for Arm span to height/length difference will be analyzed MMRM including data from Months 3, 6, 9, and 12 with gender as a covariate, subject (and/or time) as a random effect and an unstructured covariance matrix ([Section 5.2.1](#)).
- Intercurrent events and missing data: Data after study drug discontinuation and rescue will be excluded; intermediate missing values will not be imputed.
- The sample size, mean, standard deviation, median, minimum, and maximum at the baseline and postbaseline visits for observed standing height and change from baseline will be presented for each treatment arm.

The least-squares (LS) means, the 95% confidence interval for the LS means, the difference between the LS means for each pair of treatment groups, and the corresponding 95% confidence interval will be presented for change from baseline in standing height for all postbaseline visits.

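### The SAP gives conflicting models for height growth and arm span (age covariate, random effect), and the Appendix 4 code does not fit the model in SAP 5.2.1

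*SAP*

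**What the plan says.** - **Estimands.** SAP 2.1.1 summarises the primary endpoint as "Mean Height growth at 12 months adjusted for age and gender". SAP 2.1.2 summarises the secondary as "Mean change-from-baseline of arm span/standing height difference at 12 months adjusted for age and gender".
- **General model.** SAP 5.2.1: "The fixed effects of treatment, visit, treatment-by-visit interaction, age and gender will be included". It puts an unstructured covariance on the model errors. If the model does not converge, it allows compound symmetry, and visit as a continuous covariate.
- **Primary analysis.** SAP 6.1.1.1 cites 5.2.1 but asks for an MMRM "with gender (and possibly age) as a covariate, subject (and/or time) as a random effect", with an unstructured covariance matrix.
- **Secondary analysis (arm span minus height).** SAP 6.2.1.1 also cites 5.2.1, but has "with gender as a covariate, subject (and/or time) as a random effect".
- **Interim analysis.** SAP 7.2 has the same clause as 6.2.1.1, for both endpoints, and again cites 5.2.1.
- **Appendix 1.** The main model for both endpoints has time, dose, gender and age, with no dose-by-time term.
- **Appendix 4.** The code is stated to serve both endpoints. Its fixed effects are dose, month, gender and age. Its covariance line is "random int month / type=un sub=subject", and its means are requested by dose alone.
- **Protocol 9.4.2 and 9.4.3.** Both endpoints are analysed by ANOVA with terms for dose groups only.

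No text says which of these governs, or what rule decides whether age is used.

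**The concern.** The one-sided 0.017 test of height growth should rest on a single estimate fixed in advance. Here at least two covariate sets can be defended from the SAP's own words, and the covariance structure is also left open.

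The choice could be made with outcomes in view. Doses are open-label except to the anthropometrist (protocol 6.3), and the six-month interim reports heights by arm for internal decisions (SAP 7.1, 7.2).

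Age can also differ between arms. Enrolment is staggered by descending age and ascending dose, and protocol 2.2.1 reports 14, 15 and 3 children in the low, medium and high arms at September 2021.

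The code matters in its own right. If run as printed, it does not estimate the Month 12 mean that the estimand names. A convergence failure caused by its covariance line could also trigger the fallbacks in 5.2.1 for no reason in the data.

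**Working it through.** **1. The plan's own figure.** Inputs from protocol 9.2: 15 evaluable per dose, variability 0.15 (no unit given; read here as an SD on the ratio scale), 50% above reference (ratio 1.5 against 1), one-sided 0.05/3 = 0.0167, rounded to 0.017.

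- SE of a dose mean = 0.15/√15 = 0.0387.
- 0.5/0.0387 = 12.9, so power is about 100%. The stated figure of over 90% holds as a lower bound, and power is still 92% at an SD of 0.5.
- The age question therefore changes neither power nor sample size.

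**2. Covariance parameters in Appendix 4.** Month is a class variable with four levels (Months 3, 6, 9, 12).

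- Random effects: 1 intercept + 4 months = 5. Unstructured: 5×6/2 = 15. With the residual: 16.
- Distinct variances and covariances among four visits: 4×5/2 = 10, so six parameters are not identified.
- At the interim, with two visits: 3×4/2 + 1 = 7 parameters against 2×3/2 = 3.

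**3. Fixed effects in Appendix 4.** Without dose-by-month, the fitted profiles of the three doses are parallel. The dose least-squares mean is then the dose effect plus the average of four month effects, that is, a mean over Months 3 to 12. It equals the Month 12 mean only if the ratio does not change over time. SAP 5.2.1 requires the interaction and estimates at each visit.

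**4. How far age can move a dose mean.** Shift = (slope of the ratio on age) × (dose mean age minus overall mean age). Slopes and imbalances are assumptions.

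- 0.01 per year × 0.5 year = 0.005, or 0.13 SE.
- 0.02 per year × 1 year = 0.02, or 0.52 SE.
- 0.05 per year × 1 year = 0.05, or 1.29 SE.

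For scale, significance needs a ratio about 0.085 to 0.091 above 1.

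**5. Familywise error.** Simulated Month 12 linear model: three arms of 15, SD 0.15, age SD 2.2 years within the age limits, true ratio 1 at age 6.5, rejection if any dose has p < 0.05/3. There were 6,000 trials per row, with Monte Carlo SE about 0.003.

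| Age slope per year | Arm mean ages | Gender only | Gender + age | Smaller p of the two |
|---|---|---|---|---|
| 0 | 6.5, 6.5, 6.5 | 0.053 | 0.053 | 0.058 |
| 0 | 7, 6.5, 6 | 0.050 | 0.048 | 0.056 |
| 0 | 7.5, 6.5, 5.5 | 0.042 | 0.045 | 0.053 |
| 0.02 | 7, 6.5, 6 | 0.051 | 0.051 | 0.065 |
| 0.02 | 7.5, 6.5, 5.5 | 0.072 | 0.057 | 0.089 |
| 0.05 | 7.5, 6.5, 5.5 | 0.141 | 0.068 | 0.171 |

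Separate runs of 8,000 trials gave 0.056 to 0.057 for the smaller p with equal ages and no slope. With mean ages of 8, 6.5 and 5 and no slope they gave 0.063 to 0.069.

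In the last row the gender-only model is already at 0.141 before any choosing, so most of that excess is bias from omitting age. The adjusted model's 0.068 arises because the true ratio is 1 at exactly 6.5 years, while the least-squares means are taken at each sample's own mean age.

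**The case against.** The case for leaving the plan alone has real weight.

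- **Age is not simply missing.** A reader might infer from 6.2.1.1 and 7.2 that age was dropped. Both cite 5.2.1, which includes it, and Appendix 1 and Appendix 4 include it for both endpoints. Most of the SAP points to adjustment. This stands: the fault is a contradiction, not an absent covariate.
- **The primary ratio is already standardised.** Observed growth is divided by expected growth for the child's age and gender (SAP 2.1, Appendix 2.2). A reader might infer that the primary estimate is unadjusted if age leaves the model. It is not; only a residual age effect remains. This does not help the arm span-height difference, which has no such standardisation.
- **The error-rate argument is narrow.** The 0.017 rule in SAP 5.1 concerns height growth. Arm span has no alpha, and SAP 7.1 rules out stopping for futility or success and sample size re-estimation. This stands.
- **Serious inflation needs strong assumptions.** The staggered enrolment might suggest large age gaps between arms, but the documents give no arm ages and no age slope.
- **The over-parameterised code may still fit.** If it converges, it spans the same marginal covariance as an unstructured error matrix. That is true, but convergence is not assured, and it does not cure the missing interaction or the averaging over visits.

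The cross-reference to 5.2.1 does not settle the matter, because 6.1.1.1 cites that section while making optional what it makes mandatory. Appendix 4 cannot serve as tie-breaker, since it departs from 5.2.1 itself.

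**Conclusion.** The concern holds as an unresolved conflict between sections plus a coding fault. The sections that define the three analyses disagree with 5.2.1, both appendices and the estimands on age. They leave the random effect open, and the protocol still describes a dose-only ANOVA.

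For the primary test, choosing between the two covariate sets after seeing the data costs roughly half a percentage point to one percentage point of familywise error when arm ages are equal. Larger figures depend on assumed age gaps or slopes. For arm span the consequence is a less well-defined estimate, not an inflated test. A reader might infer that the trial is underpowered or its error control broken; neither follows.

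The Appendix 4 findings rest on counting parameters and reading the model statement, and need no assumption beyond month being a class variable, as coded. The correction should be made, at moderate priority.

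**What to change.** Before database lock:

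1. In SAP 6.1.1.1, 6.2.1.1, 7.2, Appendix 1 and Appendix 4, state one model: fixed effects for dose, visit, dose-by-visit, gender and continuous baseline age, with an unstructured covariance for the within-child errors. Delete the words that make age and the random effect optional, and remove the separate random-effect clause.
2. In Appendix 4, use `model ... = dose month dose*month gender age`, `repeated month / type=un subject=subject` and `lsmeans dose*month`. Test the Month 12 estimates; for height growth, against a ratio of 1.
3. In 6.2.1.1, add the baseline arm span-height difference as a covariate. This is a gain in precision from data already collected; the estimand does not require it.
4. Reconcile protocol 9.4.2 and 9.4.3 with this model. Protocol section 9 and SAP section 2 both say that major changes to the primary analysis will also appear in a protocol amendment.

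The cost is edits to the SAP and code, the matching protocol wording, and one or two degrees of freedom. Sample size and visits do not change.
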